Title: Operant Conditioning of Loading Response During Locomotion in Able-bodied Individuals and People After Stroke

NCT number: Not available

Date: April 11, 2022

Statistical Design and Power

Sample Size. 15 individuals with no known neurological conditions or history of orthopedic injuries will be studied in Aim 1. For the primary measure (soleus EMG response), the difference between the non-perturbed and perturbed EMG will be assessed by Student's *t*-test. In the previous study [29], a group analysis with a s.d. of 0.87% change (% non-perturbed EMG) was observed in the soleus EMG in response to 1 deg/s joint motion perturbation during the mid-late stance phase (i.e., the variation in the soleus EMG is linearly related to the velocity and/or amplitude of the perturbations [29]). Assuming similar s.d. for the proposed study, the sample size of N=15 allows us to estimate, with a two-sided 95% confidence level each, the soleus EMG response to perturbation within a margin of error of 5.4% non-perturbed EMG.

A sample size of 5 participants with hemiparesis and gait deficits due to a stroke will be studied in Aim 2 to examine the feasibility of the proposed algorithms and device. Due to the lack of availability of data with post-stroke participants, s.d. change % unperturbed soleus EMG cannot be defined prior to conducting testing with individuals after stroke. Hence, the pilot will provide preliminary results to characterize the soleus EMG due to the applied perturbations in people post-stroke, which will facilitate hypothesis testing and inform our sample size of stroke survivors in our subsequent study.

Statistical Analysis. All statistical analyses will be performed using SAS® 9.4. For descriptive purpose, continuous data will be summarized with the number of non-missing values, mean, and standard deviation, minimum, median, and maximum and categorical data will be summarized with the number of nonmissing values and the numbers (frequencies) of values equal to each of the possible categories, unless stated otherwise. All statistical tests will be two-sided with a significance level of $\alpha=0.05$. Unless otherwise stated, no multiplicity adjustment will be applied, and no missing values will be imputed. Mixed effects model will be used as needed to assess whether the effect of our algorithm depends on other related factors, such as age

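### Does testing perturbed against non-perturbed EMG miss the trial's subject, operant conditioning?

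*SAP*

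**What the plan says.** The title of the SAP is "Operant Conditioning of Loading Response During Locomotion in Able-bodied Individuals and People After Stroke". The body is a single section, Statistical Design and Power.

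Under Sample Size:

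- Aim 1 population: "15 individuals with no known neurological conditions or history of orthopedic injuries will be studied in Aim 1".
- Primary comparison: "For the primary measure (soleus EMG response), the difference between the non-perturbed and perturbed EMG will be assessed" by a t-test.
- Variability, from a previous study: "a group analysis with a s.d. of 0.87% change (% non-perturbed EMG) was observed in the soleus EMG in response to 1 deg/s". The SAP adds that "the variation in the soleus EMG is linearly related to the velocity and/or amplitude of the perturbations".
- What the sample size is meant to deliver: an estimate of "the soleus EMG response to perturbation within a margin of error of 5.4% non-perturbed EMG", at two-sided 95% confidence.
- Aim 2: five people after stroke. It tests whether the algorithms and device are feasible and gives a first description of soleus EMG under perturbation, to help size a later study.

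Under Statistical Analysis, all tests are two-sided at 0.05. A mixed model may be used where needed to "assess whether the effect of our algorithm depends on other related factors", with age as the example.

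**The concern.** Conditioning means a change in a response brought about by training or feedback. The primary contrast asks only whether a perturbation alters soleus EMG. The SAP cites earlier work in which EMG varied with the size of the perturbation, so one would expect a non-zero difference in people who have never been conditioned. The last sentence then speaks of an effect of the algorithm, although no analysis is named as estimating one.

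Read together with the title, this suggests a trial of conditioning whose primary test can succeed when conditioning does nothing. If so, a significant result could be reported as support for the method when it shows only that the perturbation evokes a response.

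**Working it through.** **1. The plan's own figure.** The inputs are s.d. 0.87% and N=15 (Sample Size), with t(0.975, 14) = 2.145.

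- Half-width = 2.145 × 0.87 / √15 = 0.48%. With the normal quantile it is 0.44%.
- The stated 5.4% is not reproduced at 1 deg/s. It needs an s.d. of 5.4 × √15 / 2.145 = 9.75%. Under the linear relation the SAP cites, that corresponds to 9.75 / 0.87 = 11.2 deg/s (12.3 deg/s with the normal quantile). The SAP gives no such velocity.

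That is a separate matter, the velocity behind the margin. It has no bearing on which contrast is primary.

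**2. The probabilities behind the concern.** For a paired t-test with N=15, two-sided 0.05, the noncentrality is d × √15, where d is the mean evoked response in between-person SDs. The d values are assumptions; the SAP gives none.

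| d (assumed) | d × √15 | P(significant) |
|---|---|---|
| 0.5 | 1.94 | 0.438 |
| 0.78 | 3.02 | 0.802 |
| 1.0 | 3.87 | 0.949 |

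The same check in EMG units, with the s.d. of 9.75% implied by the stated margin:

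| True evoked response (% non-perturbed EMG) | P(significant) |
|---|---|
| 0 | 0.05 |
| 2.7 | 0.17 |
| 5.4 | 0.51 |
| 8.1 | 0.85 |
| 10.8 | 0.98 |

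**3. What these numbers are.** The arithmetic is right. Each row with a non-zero response is the chance of detecting a response that exists, which is power. The hypothesis tested is that the mean difference between perturbed and non-perturbed EMG is zero. When that is true, the chance of rejection is 5% (second table, first row). To call 44% to 95% a false-positive rate, one must replace that hypothesis with one of no conditioning, which the SAP does not state.

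**4. What the SAP says the test is for.** Its statements, set side by side:

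| Element | Quantity addressed |
|---|---|
| Primary measure | Soleus EMG response |
| Primary test | Perturbed against non-perturbed EMG |
| Precision of N=15 | Response to perturbation |
| s.d. input | EMG change per 1 deg/s of perturbation |
| Aim 2 pilot | EMG under perturbation after stroke; feasibility |

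All five concern the evoked response. None mentions a conditioned response, a baseline phase or a change over sessions. Operant conditioning appears in the title only.

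**5. The algorithm.** The SAP does not say what the algorithm does. It names algorithms together with the device, and the pilot built on them describes EMG under applied perturbations. The algorithm may therefore be the one that delivers the perturbation. On that reading the primary contrast does estimate its effect, and the mixed model asks whether that effect varies with age. The text does not prove this reading, but neither does it support the other one.

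**The case for a change.** The strongest reply is that naming the primary contrast is the core work of an SAP, so a document titled for conditioning should contain a conditioning contrast or say that it draws no conclusion about conditioning. A model for what modifies the algorithm's effect also presupposes that this effect is defined somewhere.

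Part of this stands. As fixed here, the primary test cannot by itself support a statement about conditioning, and the effect of the algorithm is not defined in this document.

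The rest does not carry. A title may name the wider programme, and an evoked response is a prerequisite for conditioning it. The SAP refers to Aims 1 and 2 without setting them out, so objectives and procedures evidently stand elsewhere. Whether Aim 1 includes conditioning sessions, and whether a conditioning outcome is defined, belongs to a protocol that is not at hand. A contrast of conditioned with baseline trials would presume trials the SAP does not describe, and it would replace the stated objective. Its s.d. would be √(2(1−ρ)) times that of the response: 1.0 times at ρ = 0.5 and 1.4 times at ρ = 0, where ρ is the correlation between the two measurements. The SAP has no figure for ρ. A disclaimer about conditioning would answer a claim that the SAP never makes.

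**Conclusion.** The concern does not hold. The primary test is the direct test of the quantity that the SAP sets out to estimate, and its type I error for the stated hypothesis is 5%. The 44% to 95% is power at assumed responses of 0.5 to 1.0 SD. It would measure an error only if the result were reported as evidence of conditioning, which the SAP does not propose.

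This conclusion takes the body of the SAP, rather than its title, as the statement of what Aim 1 tests, and it treats the missing account of the aims as protocol matter. A protocol that named conditioning as the hypothesis of this very test would reopen the question. The undefined effect of the algorithm is a looseness of wording in an optional secondary model. Defining it would help the reader but would change no primary result.

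### Does naming only Student's t-test for perturbed versus non-perturbed EMG in the same 15 people commit the plan to an unpaired primary analysis?

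*SAP*

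**What the plan says.** The Sample Size paragraph under Statistical Design and Power describes a single group for Aim 1: "15 individuals with no known neurological conditions or history of orthopedic injuries will be studied in Aim 1". The primary measure is the soleus EMG response, and the only statement of the test is that "the difference between the non-perturbed and perturbed EMG will be assessed by Student's *t*-test".

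The sample size rests on precision, not power. From an earlier study, the SAP takes "a group analysis with a s.d. of 0.87% change (% non-perturbed EMG) was observed in the soleus EMG in response to 1 deg/s joint motion" as the variability. It then says that N=15 estimates "the soleus EMG response to perturbation within a margin of error of 5.4% non-perturbed EMG", "with a two-sided 95% confidence level each".

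The Statistical Analysis paragraph adds a two-sided 5% level and a mixed effects model, where needed, for factors such as age. Neither paragraph says whether the t-test is paired, one-sample or two-sample. Neither states the scale on which the test acts, a power, a target effect or a within-person correlation.

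**The concern.** Two conditions are compared and the test is named without a qualifier. Many readers take an unqualified Student's t-test between two conditions to be the equal-variance, independent-samples test, here with 28 degrees of freedom. Yet the conditions appear to come from the same 15 people, and the precision statement uses the s.d. of a change, which is a within-person quantity with 14 degrees of freedom.

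If the independent-samples form were used, the damage would depend on the scale:

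- **Raw EMG.** Differences in EMG amplitude between people would enter the error term. The interval would widen and power would fall.
- **EMG as a percentage of the non-perturbed value.** Every non-perturbed value is 100, so one of the two groups has no variance. The degrees of freedom would be twice what the data support, and the test would be slightly anti-conservative.

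In either case the primary analysis would not match the quantity on which N=15 was justified.

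**Working it through.** **Inputs from the SAP:** N=15 in one group; s.d. 0.87 (% of non-perturbed EMG) at 1 deg/s; two-sided 95% confidence; margin of error 5.4%. **Assumed:** both conditions are measured in each person, and the within-person correlation ρ between conditions is varied from 0 to 0.9.

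**1. The plan's own margin of error.** For a paired or one-sample interval the half-width is t(0.975, 14) × s.d./√15 = 2.145 × 0.87/3.873 = 0.48. For two samples of 15 it is 2.048 × 0.87 × √(2/15) = 0.65. Neither gives 5.4. The one-sample form gives 5.4 if the s.d. is 5.4 × 3.873/2.145 = 9.75, which is 11.2 times the s.d. at 1 deg/s. The SAP's remark that "the variation in the soleus EMG is linearly related to the velocity and/or amplitude of the perturbations" would allow such scaling, but the perturbation velocity is not stated. The margin therefore does not settle by its value which form was used. Its unit and its single s.d. do point to a within-person change.

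**2. Two-sample test on raw EMG: interval width.** If each condition has s.d. σ, the paired standard error is σ√(2(1−ρ)/15) and the two-sample one is σ√(2/15). The ratio of half-widths is (2.048/2.145)/√(1−ρ):

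- ρ = 0.5: 0.955/0.707 = 1.35
- ρ = 0.8: 0.955/0.447 = 2.14
- ρ = 0.9: 0.955/0.316 = 3.02

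**3. Two-sample test on raw EMG: power and type I error.** With 15 pairs and two-sided 0.05, the paired test has 80% power at a mean difference of 0.778 s.d. of the within-person differences (noncentral t). For the two-sample test at the same effect, 200,000 simulated trials per correlation gave:

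| ρ (assumed) | Power | Type I error |
|---|---|---|
| 0 | 83% | 5.0% |
| 0.3 | 71% | 2.1% |
| 0.5 | 56% | 0.8% |
| 0.7 | 28% | 0.13% |
| 0.8 | 12% | 0.02% |
| 0.9 | 1% | under 0.01% |

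More than half of the 80% is lost only somewhere between ρ = 0.5 and 0.7, and above.

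**4. Two-sample test on the percentage scale.** With one group constant at 100, the pooled standard error is √[((s² + 0)/2) × (2/15)] = s/√15, the same as in the one-sample test. Only the reference distribution differs. The true type I error is 2 × P(t with 14 df > 2.048) = 6.0%. The critical value is slightly smaller than the correct one, so no power is lost.

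**5. Which form does the text support?** The words independent, two-sample and unpaired do not appear, nor does any figure for degrees of freedom. There is one group, with one N. The primary measure is a single response, and its s.d. and margin are both expressed relative to the non-perturbed value. These features fit a paired or one-sample test and do not fit a comparison of two independent groups.

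**The case for a change.** The strongest case for a change is that naming the primary test and its scale is the SAP's own task, not something to leave to a protocol. As written, the text does not rule out the two-sample form, which is wrong for these data on either scale. N=15 is justified by a margin of error, so a half-width 1.35 to 3.02 times too large would undo that justification. A clarification would cost one sentence.

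Part of this stands. The test is not labelled as paired, its scale is not named, and the arithmetic for the misuse is correct. But the heavy loss of power needs three things together: an unpaired test, raw EMG, and a within-person correlation of roughly 0.7 or more. The SAP states none of them. The only scale that it does state is the percentage one, on which the consequence is 6.0% against 5%. The 80% is also a reference value chosen for the comparison, since the SAP plans for precision and sets no power that could be lost. Most importantly, the sentence that would be added describes the analysis to which the paragraph already leads.

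**Conclusion.** No change follows. The plan leaves a label out; it does not choose a wrong test. Student's t-test covers the paired and one-sample forms, and the single group of 15, the single response, and the s.d. and margin in percent of non-perturbed EMG make that form the natural reading.

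If the test were nonetheless run as two-sample on raw EMG, power would fall from a reference 80% to about 71%, 56%, 28% or 12% at assumed correlations of 0.3, 0.5, 0.7 or 0.8. On the percentage scale, the type I error would be about 6%. These figures describe a misreading, not the plan.

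The conclusion assumes that every participant is measured under both conditions, as the percentage scale implies, and that the analyst reads the test sentence together with the rest of its paragraph. It does not depend on the 5.4% margin, which cannot be reproduced from the stated s.d. without a perturbation velocity; that is a separate matter.

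### The 5.4% margin of error given for N=15 in Aim 1 does not follow from the printed s.d. of 0.87%, which gives 0.48%

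*SAP*

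**What the plan says.** Everything relevant stands in the Sample Size paragraph of the SAP's Statistical Design and Power section.

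- Sample: "15 individuals with no known neurological conditions or history of orthopedic injuries will be studied in Aim 1".
- Primary measure and test: for the soleus EMG response, "the difference between the non-perturbed and perturbed EMG will be assessed by Student's" t-test.
- Variability, from a previous study: "a s.d. of 0.87% change (% non-perturbed EMG) was observed in the soleus EMG in response to 1 deg/s joint motion perturbation". A parenthesis adds that "the variation in the soleus EMG is linearly related to the velocity and/or amplitude of the perturbations".
- Assumption carried forward: "Assuming similar s.d. for the proposed study".
- Confidence level: the planned sample "allows us to estimate, with a two-sided 95% confidence level each".
- Result: the precision claimed for N=15 is to know "the soleus EMG response to perturbation within a margin of error of 5.4% non-perturbed EMG".

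The SAP gives no planned perturbation velocity or amplitude, no scaled s.d. and no multiplier.

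**The concern.** The s.d. and the margin are in the same unit, percent of non-perturbed EMG. A 95% margin for a mean from 15 people is a little over half of one s.d. (2.145/√15 = 0.55). A margin of 5.4% beside an s.d. of 0.87% is about six s.d.s (5.4/0.87 = 6.2), which no 95% interval for a mean of 15 can be.

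This margin is the only quantitative basis the SAP gives for N=15 in Aim 1. Taken as printed, 3 participants would already do better than 5.4%, so the sentence does not explain why 15 were chosen. If an unstated scaling was applied, the precision depends directly on a perturbation setting that the sentence does not name, and a reader cannot tell what precision the trial is designed to reach.

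**Working it through.** **Inputs, all from the Sample Size paragraph:** N = 15; s.d. = 0.87% at 1 deg/s; two-sided 95% confidence; stated margin 5.4%.

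**Assumption:** 0.87% is the between-participant s.d. of a within-participant percentage change, so the interval is one-sample or paired with 14 degrees of freedom. The SAP says only Student's t-test; the independent-samples version is in the table below.

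**Step 1: try to reproduce 5.4%.** Margin = t(0.975, 14) × s.d./√N.

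- With t: 2.1448 × 0.87/√15 = 0.482%.
- With z: 1.96 × 0.87/√15 = 0.440%.
- Ratio of stated to computed: 5.4/0.4818 = 11.2 (t); 5.4/0.4403 = 12.3 (z).

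**Step 2: try other readings of the same inputs.**

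| Variant, s.d. = 0.87% unless noted | Result (%) |
|---|---|
| Full interval width instead of half | 0.96 |
| Two independent samples of 15 | 0.65 |
| s.d. of the difference taken as √2 × 0.87 | 0.68 |
| Bonferroni over 2 to 10 intervals | 0.56 to 0.75 |
| Division by √15 omitted | 1.87 |
| 95% prediction interval for one person | 1.93 |
| Decimal slip, s.d. = 8.7% | 4.82 (t), 4.40 (z) |

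None gives 5.4%. The Bonferroni row was tried because the SAP attaches the confidence level to each estimate; its Statistical Analysis paragraph states no multiplicity adjustment by default.

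**Step 3: s.d. needed for 5.4% at N=15.** s.d. = margin × √15/quantile.

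- With t: 5.4 × √15/2.1448 = 9.75%. For a margin that rounds to 5.4 (5.35 to 5.45): 9.66% to 9.84%.
- With z: 5.4 × √15/1.96 = 10.67%. Same rounding: 10.57% to 10.77%.

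Rounding does not close the gap to 0.87%.

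**Step 4: test the scaling reading.** Suppose 0.87% is a value per deg/s and the s.d. grows in strict proportion to velocity. Then 5.4% corresponds to 9.75/0.87 = 11.2 deg/s (t) or 10.67/0.87 = 12.3 deg/s (z). Allowing for rounding of both printed figures, the ranges are 11.04 to 11.38 and 12.08 to 12.45 deg/s, and neither contains a whole number. At 11 deg/s the t margin is 5.30%; at 12 deg/s the z margin is 5.28%.

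Under this assumption the t margin is 0.482% × velocity: 2.41% at 5 deg/s, 4.82% at 10 and 9.64% at 20. These velocities are illustrations and do not come from the SAP.

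**Step 5: what the unscaled s.d. would require.** With 0.87% and the t quantile, N=2 gives 7.82%, N=3 gives 2.16% and N=4 gives 1.38%. Three participants would therefore meet 5.4%.

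**The case against.** The strongest reply is that the text itself points to scaling. The SAP ties 0.87% to 1 deg/s and at once adds that the variation is linear in velocity and/or amplitude. That remark has little purpose unless 0.87% is a per-unit value to be multiplied up, and the assumption of similar variability can then mean similar per deg/s. The planned perturbation may be given in the protocol, which is not at hand, and a SAP may properly leave it there. On this view no miscalculation has been shown, only an unprinted step. On the literal reading, moreover, precision is better than stated, so N=15 is ample.

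Much of this stands. Scaling is plausible, 5.4% may be correct under it, and nothing here counts against N=15. Scaling by amplitude, or to a velocity that is not a whole number, cannot be excluded either.

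It does not remove the defect. The point is not that a device setting is missing from the SAP. The SAP prints an s.d., says it assumes a similar one, and prints a margin that this s.d. does not produce. A velocity stated elsewhere would help a reader guess the missing step, but the sentence would still name the wrong s.d. for its result.

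**Conclusion.** The point holds. From the inputs printed, the two-sided 95% margin is 0.48% (t) or 0.44% (z), against 5.4% stated: a factor of 11.2 or 12.3. The stated figure needs an s.d. of about 9.75% (t) or 10.67% (z), and none of the variants tried recovers it.

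The SAP does not settle whether the margin is wrong or an unprinted scaling lies behind it. That 5.4% is not reproducible as written is certain; that it is a wrong number is not. The calculation assumes a one-sample or paired interval on 14 degrees of freedom, but the conclusion does not depend on this, since two independent samples give 0.65%. The margins by velocity assume strict proportionality and serve only as illustration.

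This should be fixed, because the figure is the SAP's only quantitative support for the Aim 1 sample size. It does not threaten the validity of the trial.

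**What to change.** Keep N=15. Go back to the sample-size calculation and establish which s.d. was entered. Then:

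- Replace the assumption of a similar s.d. with the s.d. actually used, and state the perturbation velocity and/or amplitude it refers to. If it was scaled from 0.87%, give the multiplier.
- Recompute the margin as t(0.975, 14) × s.d./√15, in line with the planned t-test. If the s.d. used was near 9.75%, 5.4% stands. If 5.4% was obtained with the normal quantile (s.d. about 10.67%), the t-based margin is 2.1448 × 10.67/√15 = 5.91%, which is 9.4% wider.
- Print 0.48% only if it is confirmed that 0.87% was meant to apply unscaled. In that case also say why 15 participants were chosen.

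The cost is SAP wording and one figure, with no additional participants and no change to the analysis.

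### Is it a fault that the SAP will use data from only five stroke participants to inform the size of the next study?

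*SAP*

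**What the plan says.** All the relevant text is under Statistical Design and Power.

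- **Size and purpose of Aim 2 (Sample Size, second paragraph).** "A sample size of 5 participants with hemiparesis and gait deficits due to a stroke will be studied in Aim 2", and the reason follows at once: "to examine the feasibility of the proposed algorithms and device".
- **Why there is no calculation.** Post-stroke data are lacking, so "s.d. change % unperturbed soleus EMG cannot be defined prior to conducting testing with individuals after stroke".
- **What the pilot is for afterwards.** It gives preliminary results on the soleus response in stroke, "which will facilitate hypothesis testing and inform our sample size of stroke survivors in our subsequent study".
- **What will be reported (Statistical Analysis).** Continuous data are summarised by the number of non-missing values, mean, s.d., minimum, median and maximum.
- **Testing.** "All statistical tests will be two-sided with a significance level of" 0.05. The one test named for the primary measure, Student's t-test, appears in the Aim 1 paragraph. The Aim 2 paragraph names none.

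**The concern.** The SAP says the s.d. is missing, then offers a five-person pilot as the way forward and mentions the next sample size in the same breath. It is natural to read this as a plan to take the s.d. from five people and put it straight into a power calculation.

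That practice has a known weakness. A small-sample s.d. is imprecise and right-skewed, so it falls below the true value more often than above it, and a study sized on it tends to be too small. The SAP lists the s.d. as an output but gives no interval for it and no rule for inflating it, whereas Aim 1 receives a stated margin of error. The general 0.05 rule also carries no exception for Aim 2, where five participants could detect only a very large effect.

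If the reading were right, the stake would be a follow-up stroke study with less power than planned, and perhaps a non-significant pilot test misread as no response.

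**Working it through.** **The plan's own figure.** Aim 2's n = 5 is stated without an s.d., effect size, power or precision target, so there is no calculation to reproduce. The only calculated figure in the document, the 5.4% margin, concerns the 15 able-bodied participants of Aim 1 and does not enter this point.

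**Inputs.** n = 5, hence 4 degrees of freedom (SAP, Sample Size). Two-sided alpha 0.05 (SAP, Statistical Analysis), assumed to carry over to the next study. Also assumed, because the SAP does not give them: normal data, a paired or one-sample follow-up, 80% planned power, and a known true effect of 0.3, 0.5 or 0.8 s.d.

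**Step 1: precision of the s.d.** The 95% limits are s × √(4/χ²) on 4 df:

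- lower multiplier, √(4/χ²₀.₉₇₅) = 0.599
- upper multiplier, √(4/χ²₀.₀₂₅) = 2.874

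The ratio of the limits is 2.874/0.599 = 4.8, which is where a factor of about 5 comes from. Relative to the estimate itself, the true value could be lower by a factor of 1/0.599 = 1.7 or higher by a factor of 2.9. Required N scales with the square: 0.36 to 8.3 times.

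**Step 2: chance that the s.d. is too small.** P(s < σ) = P(χ²₄ < 4) = 1 − 3e⁻² = 0.594. This comes from skewness, not from the width of the interval.

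**Step 3: power of a follow-up sized on the bare point estimate.** By normal approximation, true power = Φ((1.96 + 0.84) × s/σ − 1.96). Over 400,000 draws of s:

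- mean 68%, median 73%
- below 80% in 59.5% of draws, below 50% in 26%

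Exact t-based sizing at true effects 0.3, 0.5 and 0.8 s.d. gives mean power 68%, 69% and 70%, with a shortfall in 58–60% of cases. The assumed effect hardly matters.

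**Step 4: the same exercise under a different rule.** Sizing on the one-sided 80% upper limit multiplies s by √(4/χ²₀.₂₀) = 1.56. At a true effect of 0.5 s.d. mean power becomes 89%, below 80% in 20% of pilots and below 50% in 6%. The price is N larger by 1.558² = 2.43. Since E(s²) = σ², point-estimate sizing asks for about the right N on average. The upper-limit rule asks on average for about 2.4 times the N needed, and for more than 4 times in P(χ²₄ > 6.58) = e⁻³·²⁹ × 4.29 = 16% of pilots.

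**Step 5: compare with the text.** Steps 3 and 4 give different answers only because the sizing rule differs, and the SAP states neither rule. It says the pilot will inform the next sample size. It does not say that the observed s.d. will be used alone, that no other data will be consulted, or that the next design will have no sample-size re-estimation. Both power results describe a document that is not this one.

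**Step 6: the testing rule.** With n = 5, a paired t-test at two-sided 0.05 has 80% power only for an effect of about 1.68 s.d. or more. The figure is correct but has no target. The t-test is tied to Aim 1, and the mention of hypothesis testing in Aim 2 stands beside the subsequent study and reads most naturally as referring to it. A sentence fixing the level for whatever tests are run does not create one for Aim 2.

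**The case for a change.** The best case for the concern is that the SAP itself makes the link. It names the s.d. as the missing quantity, follows with a consequence clause, and offers the pilot as the source. The only summary it fixes is a bare s.d. An interval and a sentence on carrying the uncertainty forward would cost almost nothing and need no extra participants, and how an s.d. is reported is SAP content.

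Part of this stands. The s.d. from Aim 2 will be weak evidence, and whoever designs the next study should not take it at face value. A line giving its confidence interval, or a label calling Aim 2 estimation only, would be harmless.

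It does not amount to an error here. The interval in Step 1 can be computed by any reader from the n and s.d. that the SAP already reports, so its absence hides nothing. How much to inflate is a trade-off between the risk of low power and a study about 2.4 times larger than needed on average. Reasonable statisticians differ on it, and those planning the later trial will be better placed to decide. The estimation-only label would clarify the plan but correct no contradiction, since no Aim 2 test is specified.

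**Conclusion.** No fault in this plan. Five participants are offered for feasibility, and nothing in the document suggests that number is wrong for that purpose. The SAP openly says it has no stroke s.d. to plan with and claims only preliminary results.

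The imprecision is real: 0.60 to 2.87 times the estimate at 95%, and a 59% chance of an s.d. that is too low. The loss of power, about 68–70% on average against 80% planned, follows only if a later team sizes its study on the unadjusted point estimate. That is a conditional statement about another trial, resting on assumed normal data, a paired design and a known effect. Even then, the 59/41 split counts every shortfall below 80%, however slight.

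Carried out exactly as written, the SAP gives the same results and the same conclusions for Aim 1 and Aim 2 whether or not an interval or an inflation rule is added. The point is advice for the next study's sample-size section.

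### Does the open-ended mixed-model sentence on effect modifiers need to be rewritten to limit false findings?

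*SAP*

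**What the plan says.** The SAP has one section, Statistical Design and Power, with a Sample Size part and a Statistical Analysis paragraph.

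- **Primary analysis (Sample Size).** "For the primary measure (soleus EMG response), the difference between the non-perturbed and perturbed EMG will be assessed by Student's" *t*-test. There is one primary measure and one test for it.
- **Participants (Sample Size).** "15 individuals with no known neurological conditions or history of orthopedic injuries will be studied in Aim 1"; "A sample size of 5 participants with hemiparesis and gait deficits due to a stroke will be studied in Aim 2". Aim 2 is described as a pilot on feasibility.
- **Error rates (Statistical Analysis).** "All statistical tests will be two-sided with a significance level of" 0.05. "Unless otherwise stated, no multiplicity adjustment will be applied, and no missing values will be imputed". No exception is stated anywhere.
- **Effect modification (Statistical Analysis, last sentence).** "Mixed effects model will be used as needed to assess whether the effect of our algorithm depends on other related factors, such as age". The public copy ends there without a full stop, so text may have followed.

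The only other mention of an algorithm is in the Aim 2 feasibility statement, where the word is plural and no outcome is attached.

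**The concern.** Three things are open in the modifier sentence. The algorithm's effect is not equated with the primary contrast, so the outcome, the unit of analysis (person or step) and the random terms are unstated. Running the model is left to judgement, with no criterion. The factor list has one member and an invitation to add more. All tests are at two-sided 0.05 without adjustment, and the analysis carries no exploratory label.

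If analysts tried several factors or several models after seeing the data and reported what was significant, a reader could not tell a real age effect from a product of the search. With 15 people the data could do little to settle the matter. At stake is a secondary statement about who responds, not the primary result.

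**Working it through.** **The plan's own figure.** The Sample Size text gives a margin of error of 5.4% of non-perturbed EMG at N=15, after quoting an SD of 0.87% for a 1 deg/s perturbation. The t-based half-width from that SD is 2.145 × 0.87/√15 = 0.48%, so 5.4% is not reproduced. It would need an SD of 5.4 × √15/2.145 = 9.75%, which is linear scaling to about 11.2 deg/s, a step the SAP does not show. This is a separate matter. It does mean that a confidence interval for an age slope cannot be sized reliably: the half-width per SD of age, 2.160 × SD/√14, is 5.6% with SD 9.75% and 0.50% with SD 0.87%.

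**False modifiers.** Inputs: alpha 0.05 two-sided and no adjustment (Statistical Analysis paragraph); number of factors k, not given and therefore assumed from 1 to 10. For independent tests the chance of at least one false modifier is 1 − 0.95^k. The last three columns are null simulations (40,000 runs, one response per person, t reference).

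| k | Formula | n=15 | n=100 | n=15, factors correlated 0.6 |
|---|---|---|---|---|
| 1 | 5.0% | 5.1% | 5.0% | 4.8% |
| 3 | 14.3% | 14.4% | 14.2% | 12.3% |
| 5 | 22.6% | 22.7% | 22.4% | 17.3% |
| 10 | 40.1% | 39.9% | 40.3% | 26.8% |

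The inflation comes from the number of tests, not from the sample size. N=15 adds to it only if a large-sample z reference is used: 7.2% for one factor and about 20% for three. The SAP does not call for that reference.

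**Sensitivity at N=15.** With t(0.975, 13) = 2.160, a correlation is significant when |r| > 2.160/√(2.160² + 13) = 0.514. Simulated power is 19% at r=0.3, 50% at r=0.5 and about 80% at r=0.65. This shows a weak secondary analysis. It does not bear on the false-positive rate.

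**What the wording settles.** Asking whether an effect "depends on other related factors, such as age" is asking for an interaction. A main effect of age on EMG is not a natural reading. The only effect for which the SAP defines a contrast and a test is perturbed versus non-perturbed soleus EMG, so a condition-by-factor interaction on that contrast is the obvious model.

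**The case for a change.** The strongest case for a change is that even one test of age is safe only under a correctly built model, and the SAP builds none. Suppose steps are analysed individually with a random intercept per person but no random condition effect. Let f be the step noise left after averaging, as a share of the observed variance of per-person differences. Type I error is then about 2Φ(−1.96√f): 54% at f=0.10, 33% at 0.25, 17% at 0.50 and 9% at 0.75. As an example, take 50 steps per condition, a step SD of 20% and a total SD of 9.75% (variance 95). Then f = (2 × 400/50)/95 = 0.17, and the formula gives 42%; simulation gave 41.5%, against 5.3% for a per-person analysis. A rewrite would cost only words.

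The arithmetic stands once f is defined this way, but it measures a misspecified model that the SAP nowhere describes, with step counts and step SDs that the SAP does not give. An analyst who fits a mixed model to ask whether a condition effect varies with a person-level factor would normally let that effect vary by person, or regress per-person differences on the factor. The two agree when step counts are balanced.

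It also stands that the sentence does not identify one analysis and does not label it exploratory. Its status is nevertheless clear from the structure: one measure is called primary and has its own test, and the modifier model is an optional extra. The missing full stop cuts both ways: lost text might have held factors or model terms, so nothing here relies on it.

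**Conclusion.** No change to the plan is called for. The gap is real but minor: the effect, the occasion for the model and the factors beyond age are left to the analyst. The chance of at least one false modifier is 5% if age alone is tested once, and about 14% for three independent factors, at any sample size. The higher figure rests on an assumed count, independent factors, one test per factor and a t-type reference; correlated factors lower it.

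Writing down a definition, a factor list and an exploratory label would record what a competent analyst would do anyway. It would not correct a stated rule that gives a wrong answer. Leaving a secondary analysis unadjusted, and saying so, is an ordinary trade-off in a study of 15 participants plus a pilot of 5. Any modifier result should be read as exploratory and alongside the number of factors examined. The primary *t*-test is untouched.
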